#### **3.1 Background and Ratio**

The RehaClinic Kilchberg is a neurological rehabilitation facility with phases B-D. Between February and the end of March, out of 78 patients, 71% were stroke patients. Therefore, my choice of topic for the Master's thesis fell on the stroke. Sufficient patients should be recruited for the study period from July to the end of September. The duration of the study is based on the timetable for the Master's thesis. Initially, 20 stroke patients will be recruited. Once the number has been reached, the study is completed in order to be able to start with the descriptive statistics and to analyze potential BIAS.

The main purpose of the study is to determine if there is a difference in effect size when comparing single-balance training to group-balance training. Since only 7% of inpatient rehabilitation patients were able to climb stairs at discharge and had reached sufficient walking speed to be safe and independent in everyday mobility (Balasubramanian, Clark, & Fox, 2014), the primary outcome is walking speed. It is determined with the 10m walk test. The secondary outcome of balance is captured by the Berg Balance Scale. The ability to walk is determined by the FAC.

Deficits in the vestibular, visual, motor, and / or somatosensory systems lead to falls in the first 6 months after the stroke. This affects approximately 46% of patients (Mackintosh, Hill, Dodd, Goldie, & Culham, 2005). But also cognitive processes such as attention and concentration play an important role. Therefore, the treatment must be adapted to the respective strategy of the patient. If the patient increasingly uses the visual system, the therapy has to work a lot with the

eyes closed. In turn, if he uses more of the sensorimotor system is increasingly trained with unstable documents (Mehrholz, Ada, Dean, Dettmers, & Dohle, 2011). After this system, the balance program was set up. It is the same for the intervention and control group to make a difference between individual and group training. The group size results from the specification of the RehaClinic Kilchberg with a number of participants between 3-6 patients. The group will not exclusively include stroke patients, since the participants in rehabilitation routine are otherwise mixed up by the diagnoses. In most cases, stroke, Parkinson's, craniocerebral trauma and also tumor patients participate.

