## **4 GOAL OF THE STUDY**

### **4.1 maingoal**

The study is part of my master thesis. But it has found so much interest in my superiors that they would possibly perform as a larger-scale RCT. Therefore, it is designed as a pilot study to detect any occurring BIAS and to be able to calculate a sample size, which will be necessary to be able to make a statement.

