### **4.2 Primary goal**

Improvement of walking speed in stroke patients in inpatient rehabilitation through balance training. Determine if there is a difference in effect size between individual and group balance training.

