## **10 STATISTICS**

One aim of this pilot study is to determine an appropriate number of cases. Therefore, with the obtained data set using G \* Power Ver. 3.1.9.2 the SampleSize is calculated.

Further descriptive statistics are done with SPSS version 25. The mean values for each assessment are calculated. The absolute and relative frequencies are calculated. To determine the scattering parameters, the standard deviation is determined.

To determine if there is a difference between intervention and control group, first the odds ratio is shown.

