### **10.1 Hypothesis**

Zero Hypothesis: individual balance training is more effective in stroke patients to improve walking speed than group balance training.

Alternative Hypothesis: individual balance training is not more effective.

Due to the limited number of cases, however, only one guess can be made. The number of cases is limited by the time factor of the deadline for the Master thesis. I think a realistic number for recruiting is 20 patients.

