### **10.2 Sample size calculation**

It is planned to recruit 20 patients to RehaClinic Kilchberg. This results in 10 patients each for the experimental group and the control group. This number is based more on the temporal than on the statistical factor. It serves only for the descriptive statistics in order to be able to make already first assumptions and to be able to carry out a SampleSize calculation. If this number is not reached by the end of April, the pilot study will nevertheless end. This should ensure the writing of the master thesis, so that it can be delivered on time.

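### The only between-arm statistic named is an odds ratio with no event, for a continuous primary outcome, and the follow-up sample size most naturally rests on the observed pilot effect

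*Combined protocol and SAP*

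**What the plan says.** The synopsis makes gait speed by the 10 m walk test the primary outcome. Section 8.2 records it in m/s, and section 8.2.1 times it one day before the first session and one day after the last.

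Section 10 lists descriptive summaries: "The mean values for each assessment are calculated", together with frequencies and standard deviations. For the comparison of arms it has one sentence: "To determine if there is a difference between intervention and control group, first the odds ratio is shown". Section 10.3.2, headed as the primary analysis, says only who analyses and when. Sections 10.1 to 10.4 add no estimator, model or interval.

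The study's purpose is stated as an effect-size comparison, in section 3.1 ("The main purpose of the study is to determine if there is a difference in effect size") and in section 4.2 ("Determine if there is a difference in effect size between individual and group balance training"). The follow-up sample size is also an aim. Section 4.1 wants "to be able to calculate a sample size, which will be necessary to be able to make a statement", and section 10 begins its method with "Therefore, with the obtained data set using G"*Power.

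The plan is open about its limits: "Due to the limited number of cases, however, only one guess can be made" (section 10.1) and, of the 20 patients, "It serves only for the descriptive statistics" (section 10.2).

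**The concern.** An odds ratio needs a yes/no event. Sections 5.1 to 5.3 offer four thresholds: a gain of 0.18 m/s, a speed of 1.0 to 1.2 m/s, a Berg score of 45, and a speed of 0.8 m/s. None is linked to the odds ratio. The 0.18 m/s gain is the obvious candidate because it stands under the primary target, but the plan does not say so. The event could therefore be chosen after the data are seen, in an open study (6.5) whose investigator delivers the training (3.2) and does the analysis (10.3.2).

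Even with an event, the scale is wrong for the question. The study asks how far walking speed differs between arms, and an odds ratio does not estimate that. A mean difference could be worked out from the planned means, but it is not specified and baseline speed has no stated role.

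The sample-size aim inherits the problem. The calculation uses the pilot data, no planning difference is named for it, and the stated interest is an effect size. The natural reading is that the observed pilot effect goes into G*Power. An observed effect from 10 per arm is too unstable for that.

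**Working it through.** **The plan's own figure.** The pilot size of 20 (10 per arm) has no alpha, power, SD or effect behind it. Section 10.2 says that time set it, so there is nothing to reproduce and the figure is not disputed.

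**Inputs.** From the documents: 10 per arm, a continuous outcome, and possibly fewer than 20 completers (10.2 lets the study end short, 10.4 excludes incomplete cases, and 7.4 replaces withdrawals only if possible). Assumed: two-sided 5%, 80% power, 8 per arm as the reduced case, and the true effects and SDs shown below.

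**1. Information kept by a responder split.** For a normal outcome, large sample and small difference, this is φ(z_p)² / [p(1−p)].

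| Responder rate p | Information kept |
|---|---|
| 50% | 0.637 |
| 30% | 0.576 |
| 20% | 0.490 |

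**2. Chance of an empty cell**, which makes the odds ratio zero, infinite or undefined: 1 − (1 − p₁ⁿ − (1−p₁)ⁿ)(1 − p₂ⁿ − (1−p₂)ⁿ). For 30% v 50% and n = 10: 1 − 0.97175 × 0.99805 = 0.030.

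| Responder rates | 10 per arm | 8 per arm |
|---|---|---|
| 30% v 50% | 3% | 7% |
| 20% v 40% | 11% | 18% |
| 10% v 30% | 37% | 46% |

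**3. Observed effect entered in G*Power.** The chance of a wrong sign is Φ(−d/√(2/n)). For d = 0.5 and n = 10: Φ(−0.5/0.447) = Φ(−1.118) = 0.13. The N range comes from 400,000 simulated pilots per setting. Each observed unadjusted d was converted to N per arm by the noncentral t, and the percentiles are among pilots with the right sign.

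| True d | N needed per arm | Pilot per arm | Wrong sign | N per arm, 10th to 90th percentile |
|---|---|---|---|---|
| 0.3 | 176 | 10 | 25% | about 17 to 1,570 |
| 0.5 | 64 | 10 | 13% | about 13 to 670 |
| 0.5 | 64 | 8 | 16% | about 11 to 680 |
| 0.8 | 26 | 10 | 4% | about 9 to 170 |

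At d = 0.5 the upper percentiles move by some 10 to 15 patients between simulations.

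**4. Only the SD taken from the pilot, with the difference fixed in advance.** Take a difference of 0.5 true residual SDs, so that 64 per arm is again right. The pilot SD varies as √(χ²_df/df), with 17 df for a baseline-adjusted analysis of 20 completers and 13 df for 16. The upper one-sided 80% limit multiplies the SD by √(df/χ²₀.₂₀,df).

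| df | N, 10th to 90th percentile | P(N < 64) | Limit factor | N with limit, 10th to 90th percentile | P(N < 64) with limit |
|---|---|---|---|---|---|
| 17 | 39 to 93 | 53% | 1.19 | 54 to 131 | 19% |
| 13 | 35 to 97 | 54% | 1.23 | 53 to 146 | 19% |

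Steps 3 and 4 are not on exactly the same scale, since step 3 is unadjusted (18 df at 10 per arm) and step 4 uses a residual SD. The contrast of 13 to 670 with 39 to 93 is far larger than that difference.

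**5. What the follow-up table could look like**, for an assumed residual SD of 0.20 m/s (two-sample t formula with the residual SD, N per arm).

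| Between-arm difference | Pilot SD as is | Upper 80% limit, 17 df | Upper 80% limit, 13 df |
|---|---|---|---|
| 0.06 m/s | 176 | 249 | 264 |
| 0.09 m/s | 79 | 111 | 118 |
| 0.12 m/s | 45 | 63 | 67 |
| 0.18 m/s | 21 | 29 | 31 |

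**The case against.** The G*Power half is an inference. Section 10 does not say that the observed effect is entered. The pilot SD combined with an outside difference would also be a calculation from the pilot data. That stands: the documented defect is that the input is not named, and step 3 shows the cost of the most natural reading, not of a stated procedure.

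The odds ratio is only the first thing shown, beside means, SDs and frequencies, and the 0.18 m/s gain makes a responder comparison coherent. This is partly right. The raw summaries are not lost, and one linking clause would define the event. But the means are not described as a comparison of arms, no second step is named, and a defined responder odds ratio would still not answer a question posed in m/s.

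The study calls itself descriptive and says it mainly analyses bias. That is why wide intervals and the choice of 20 are not criticised here. However, section 10.2 also wants the data to allow a sample-size calculation, and a descriptive comparison still needs a defined quantity.

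Finally, baseline adjustment is not the only repair. A difference in mean change with a CI would also restore the scale. The SD-only route still falls short of the required N about half the time unless an upper limit is used.

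**Conclusion.** The concern holds and should be fixed. It is certain from the text that an odds ratio without an event is the only between-arm statistic for a continuous primary outcome. That the observed effect would drive the follow-up sample size is the most natural reading but not a stated rule.

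The main harm is the mismatch of scale. The second is that an observed effect from 10 per arm cannot reliably size a trial: N per arm could plausibly differ fiftyfold between pilots (670/13 ≈ 52) at an assumed true standardised difference of 0.5. All sizes rest on assumed effects, SDs and responder rates, because the documents give none. The feasibility and bias aims are not touched.

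**What to change.** In section 10, replace the odds-ratio sentence with text such as: *The between-group effect is the difference in mean post-training 10 m walking speed, adjusted for baseline speed (ANCOVA), with 95% CI, reported descriptively.* A difference in mean change with its CI is an acceptable alternative. If an odds ratio is kept, label it descriptive and name its event before any data are seen.

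For the sample size, state that:

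- the observed between-group effect is not entered in G*Power;
- the pilot supplies the SD that matches the planned analysis (the residual SD for ANCOVA, the change SD for change scores);
- N is tabulated over a range of between-arm differences justified in advance, with the uncertainty of the SD shown. An upper one-sided limit is one option, and its factor should be computed from the actual degrees of freedom because fewer than 20 may complete;
- alpha and power are given here or in the follow-up protocol.

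The 0.18 m/s in section 5.1 is a within-patient improvement, and both arms do the same exercises (7.5.2). It should not serve as the between-arm difference without separate justification.

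The cost is a few sentences and no new data, since baseline speed is already measured. The covariate uses one degree of freedom and the range of differences has to be argued. If the upper 80% limit is used, the follow-up trial grows by about 42% (1.19² ≈ 1.42, 17 df) or 51% (1.227² ≈ 1.51, 13 df).

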### **10.1 Hypothesis**

Zero Hypothesis: individual balance training is more effective in stroke patients to improve walking speed than group balance training.

Alternative Hypothesis: individual balance training is not more effective.

Due to the limited number of cases, however, only one guess can be made. The number of cases is limited by the time factor of the deadline for the Master thesis. I think a realistic number for recruiting is 20 patients.

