Goal:	
Goal: A suitable sample size is to be determined for a larger follow-up study and the study design should be checked for feasibility.
 
Question: In stroke patients, is there a difference between individual and group balance training in terms of improving walking speed?
 
Hypothesis: individual balance training has a better impact on walking speed than group balance training.
 
Primary outcome: gait speed → 10m walking tests
 
Secondary outcome: Berg-Balance Scale, FAC

Participants:	It will recruit 20 patients after stroke at the RehaClinic Kilchberg.
Study design:	controled, randomized, open pilot study with paralell groups - monocentric
In/Exclusion criteria:	Inclusion: min. 18 years, stroke starting from rehabilitation phase B, ability to understand therapy instructions, walkable with aids Exclusion: Neurodegenerative disease, non-stroke dizziness, cardiopulmonary insufficiency, polyneuropathy, peripheral vascular disease
Experimental intervention:	individual balance training: after the initial assessments, the three week intervention time begins, which is completed with the reassessments.  The patients receive 2x weekly individual balance training for 25 minutes each.  This runs in addition to the normal, prescribed rehabilitation program. The rehabilitation program includes at least 3 therapies daily. These may be group therapies, speech therapy, occupational therapy, neuropsychology and physiotherapy adapted to the needs of the patient. In physiotherapy and occupational therapy no balance training may be performed during the intervention period.
Controle intervention:	The patients receive 2x weekly group balance training for 25 minutes each.  This runs in addition to the normal, prescribed rehabilitation program. The rehabilitation program includes at least 3 therapies daily. These may be group therapies, speech therapy, occupational therapy, neuropsychology and physiotherapy adapted to the needs of the patient. In physiotherapy and occupational therapy no balance training may be performed during the intervention period.  In group therapy are 3 to 6 patients with different neurological diagnoses. As it is usual in rehabilitation everyday life.
Number of participants:	In total, 20 patients should be recruited. 10 in the intervention group and the other half in the control group.

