### **3 INTRODUCTION**

Every year, around 16,000 Swiss people a stroke (Meyer, Simmet, Arnold, Mattle, & Nedeltchev, 2009). This leads to the interruption of the blood supply in the brain. This can be caused on the one hand by an ischemia, or by a rupture of a blood vessel (World Health Organization, 2016). This often leads to limitations in everyday activities (Busch & Kuhnert, 2017). This is the main goal of the patient's treatment goals (Bohannon, Andrews, & Smith, 1988).

A 2014 review found that as many as 7% of inpatient rehabilitation patients were able to go upstairs on discharge and had reached sufficient walking speed to be safe and independent in everyday mobility (Balasubramanian, Clark, & Fox, 2014). In another study, 39% of stroke survivors fell (Nyberg & Gustafson, 1995).

Strokes often affect the exact systems we need for standing and aisle safety. According to Mehrholz et al. (2011) these are the vestibular, the visual, the motor and the somatosensory system. But also cognitive processes, such as attention and concentration play an important role here. Therefore, it seems likely that single-balance training is more efficient to improve walking speed. There is less distraction, with 55% of stroke patients complaining of lack of concentration (Hochstenbach, Prigatano, & Mulder, 2005), and individual instruction and external feedback promoting and supporting patient autonomy (Wulf, 2011)

In the reviews by Pollock et al (2014) or also by Dohle et al. (2016), different treatment approaches are analyzed and compared. So far, however, it has not been examined whether there is an effect difference in the intervention itself, whether this is done in individual or group settings. Therefore, in this pilot study, group balance training will be compared to single-weight training (Dohle, et al., 2016).

Therefore, a pilot study will be carried out to determine the feasibility of an RCT. This will reveal BIAS and determine the SampleSize needed to get a meaningful result.

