## **5 TARGETS OF THE STUDY**

### **5.1 Primary target**

Improving walking speed by 18 cm/sec would be a successful outcome (Fulk et al, 2011). Whether there is a difference between individual balance training and group balance training is to be determined. To be able to cross a pedestrian traffic light, a walking speed of 1.0-1.2 m/sec would be necessary (Hüter-Becker, et al., 2005). This would be the ideal value.

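### Section 10.1 labels the study hypothesis as the null, and its negation, which includes no difference, as the alternative

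*Combined protocol and SAP*

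**What the plan says.** Section 10.1 sets out the pair in two lines. The null is "Zero Hypothesis: individual balance training is more effective in stroke patients to improve walking speed than group balance training". The alternative is "Alternative Hypothesis: individual balance training is not more effective". A caution follows: "Due to the limited number of cases, however, only one guess can be made". The section then ties the number of patients to the thesis deadline.

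Two other places show which statement is the research claim. The synopsis gives as the study hypothesis that "individual balance training has a better impact on walking speed than group balance training". Section 3 argues from reduced distraction and individual instruction: "Therefore, it seems likely that single-balance training is more efficient to improve walking speed".

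Three places put the matter without a direction. The synopsis asks "is there a difference between individual and group balance training in terms of improving walking speed". Section 4.2 has "Determine if there is a difference in effect size between individual and group balance training". Section 5.1 has "Whether there is a difference between individual balance training and group balance training is to be determined".

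On analysis, section 10 lists means, standard deviations, frequencies and a G\*Power sample size calculation. It says that the difference between arms will first be shown as an odds ratio, and it names no event. Section 10.2 sets 20 patients, 10 per arm, by the time available and for descriptive use. Section 10.3 makes bias the main subject of analysis. Section 10.3.2 says only who will analyse the data and when.

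**The concern.** By convention, the claim that a study hopes to support is the alternative, and the null is what stands until the data speak against it. Section 10.1 does the opposite. Superiority of individual training becomes the default, and the absence of any difference becomes something to be demonstrated.

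If the printed pair guides the discussion, data that settle nothing leave superiority unrejected and therefore seemingly supported. A pilot with 10 patients per arm may well be inconclusive. Section 4.1 says that a larger randomised trial may follow, and section 13 says that the pilot will be published as part of the thesis, so the pair could be repeated in both. The directional hypothesis and the non-directional question also leave the number of tails for the G\*Power calculation open.

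**Working it through.** Write Δ for the true mean improvement in walking speed with individual training minus that with group training.

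**Step 1. Set the statements side by side.**

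| Place | Role given to the statement | Content |
|---|---|---|
| Section 10.1, first line | null | Δ > 0 |
| Section 10.1, second line | alternative | Δ ≤ 0 |
| Synopsis, hypothesis | study hypothesis | Δ > 0 |
| Section 3 | rationale | Δ > 0 expected |
| Synopsis question, 4.2, 5.1 | question or goal | Δ ≠ 0 or not |

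**Step 2. Compare with the conventional pair.** The study hypothesis is Δ > 0, so the directional pair should be H0: Δ ≤ 0 against H1: Δ > 0. The printed pair is its exact exchange. Both lines are swapped consistently, so one lost word does not account for it.

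**Step 3. Look for a design that would justify the order.** With a margin M, a non-inferiority null would be Δ ≤ −M, and an equivalence null would be that Δ lies at or beyond −M or +M. Neither makes Δ > 0 the null. The plan gives no margin and describes neither design.

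**Step 4. Locate no difference.** Δ = 0 falls under the printed alternative. A standard two-sample test takes its reference distribution at Δ = 0, which must therefore belong to the null. The printed pair would not fit such a test if one were added.

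**Step 5. Check whether any stated number depends on the labels.** The total of 20 (20 / 2 = 10 per arm) comes from the timetable. Means, standard deviations, frequencies and an odds ratio are the same under either labelling. No significance level, power or decision rule is given. There is no figure to reproduce, and none changes.

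**Step 6. Show what the open number of tails could do later.** This concerns the directional versus non-directional wording, not the reversal. The usual normal approximation is

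n per arm = 2 × (z for alpha + z for power)² × (SD / δ)².

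The assumptions are alpha 0.05, power 80%, and an SD of change from 0.15 to 0.40 m/s, none of which the plan gives. For δ, take 0.18 m/s from section 5.1, although that section states it as an improvement and not as a difference between arms. The squared sum is (1.960 + 0.842)² = 7.85 two-sided and (1.645 + 0.842)² = 6.18 one-sided.

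| Assumed SD (m/s) | Two-sided n per arm | One-sided n per arm |
|---|---|---|
| 0.15 | 11 | 9 |
| 0.20 | 20 | 16 |
| 0.30 | 44 | 35 |
| 0.40 | 78 | 62 |

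For SD 0.30, for example: 2 × 7.85 × (0.30 / 0.18)² = 43.6, rounded up to 44. The two-sided number is larger by 7.85 / 6.18 = 1.27, about 27% before rounding, so the choice should be stated before G\*Power is run.

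**The case against.** The strongest reply is that nothing in this pilot uses the labels. The sample is for description and for sizing a later trial, bias is the main analysis, and no test exists that could be run backwards. Section 10.1 itself limits the conclusion. The intended claim can be recovered from the synopsis. The text is also a translation, with German left in the registration note under section 2 and in the heading of 7.1.2, so a slip is plausible.

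Most of this stands, and it sets the size of the point. It does not remove it. Both labels are explicit, this is the only formal pair in the document, and no other section states it correctly. The caution in 10.1 limits how strong a conclusion may be, but does not say which claim is the default. If the cause is translation, the remedy is the same.

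Three stronger readings are tempting, and the documents support none of them:

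- A reader might infer that the reversal spoils a planned analysis or the sample size. Step 5 shows that neither depends on it.
- A reader might size the problem by how often a 95% confidence interval from 10 patients per arm would include zero. That frequency is the same whichever label each hypothesis carries. It describes the imprecision of a small pilot, which sections 10.1 and 10.2 already admit.
- A reader might argue that, with identical arms, a 5% test would retain the printed null 95% of the time. That is true of such a test, but the plan contains none.

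On the odds ratio, it is fair to add that section 10 says it is shown first and also plans means and standard deviations, so the comparison would not rest on it alone. The gap is that no between-arm difference in walking speed is named.

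**Conclusion.** The point holds as a wording error in the plan's only formal hypothesis pair. Its numerical effect on this pilot is nil. What remains is a risk of misreading: an inconclusive result taken as support for individual training, or the pair carried into the follow-up trial. For the label swap the severity is minor.

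This rests on reading the synopsis and section 3 as the statement of what the study hopes to show, and on the absence of any margin or other design that would explain the order. The sample sizes in step 6 rest on assumed values and illustrate only why the number of tails should be fixed.

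The missing between-arm estimate is linked but separate. An odds ratio needs an event, the plan names none, and walking speed is a continuous measure taken before and after the intervention.

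**What to change.** In section 10.1, swap the labels. H0: individual training is not more effective than group training in improving walking speed. H1: it is more effective. If the sponsor intends the non-directional question of the synopsis, 4.2 and 5.1, use instead H0: no difference in mean change, and H1: a difference. State the choice and use the same number of tails in G\*Power.

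As a separate change, section 10.3.2 should name the between-arm difference in mean change in walking speed (reassessment minus baseline), with a 95% confidence interval, as the main descriptive comparison. An odds ratio, if kept, needs a defined event and should be secondary.

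No new data or visits are needed. Section 12.1 requires plan changes to be signed by the sponsor investigator and submitted to the ethics committee for approval. Under section 2.8 the label swap alone could be seen as non-essential, whereas the change to 10.3.2 may count as substantial because it touches the statistical evaluation concept. A single short amendment can cover both.
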